9. STUDY FLOWCHART AND FOLLOW-UP ASSESSMENTS

Procedure	Visit 1	Visit 2	Visit 3	Visit 4	Visit 5	Visit 6	Visit 7	Visit 8
	Treatment 1 ^c	Treatment 2	Treatment 3	Treatment 4 Optional	Treatment 5 Optional	1 month Follow-up 1	3 months Follow-up 2	6 months Follow-up 3
	T ₀ ^f (± 5d) ± Δ ^{ef}	T ₀ + 4w (± 5d) ± Δ	T ₀ + 8w (± 5d) ± Δ	T ₀ + 12w (± 5d) ± Δ ^e	T ₀ + 16w (± 5d) ± Δ ^e	T ₀ + 20w (± 8d) ± Δ ^e	T ₀ + 28w (± 8d) ± Δ ^e	T ₀ + 42w (± 8d) ± Δ ^e
Max duration	-	4w+5d	8w+10d	12w+15d	16w+20d	20w+25d	28w+33d	40w+41d ~ 47w
Min duration	-	4w-5d	8w-10d	-	-	12w-15d	20w-23d	32w-29d ~28w
Subject Screening, Enrolment Procedure & Informed Consent ^g , Post treatment care instructions	X							
Facial dermatological skin examination	X	X	X	X	X	X	X	X
Inclusion/ Exclusion criteria	X							
Medical/Surgical history	X							
Demographics	X							
Limited Physical examination ^a	X							
Concomitant Therapy/Medication	X _b	X	X	X	X	X	X	X
Verbal Inquiry regarding pregnancy	X	X	X	X	X	X	X	X
Photography of Treatment Area(s) – prior to treatment	X (baseline)	X	X	X	X	X	X	X
Photography of Treatment Area(s) – After treatment			X					
Investigational/Comparator Device Treatment	X	X	X	X	X			
Subject experience and satisfaction questionnaire	X		X*	X*	X*	X*		X

Procedure	Visit 1	Visit 2	Visit 3	Visit 4	Visit 5	Visit 6	Visit 7	Visit 8
	Treatment 1 ^c	Treatment 2	Treatment 3	Treatment 4 Optional	Treatment 5 Optional	1 month Follow-up 1	3 months Follow-up 2	6 months Follow-up 3
GAIS Assessment		X	X	X	X	X	X	X
FWCS Assessment	X _f	X	X	X	X	X	X	X _f
WAS Assessment	X _f	X	X	X	X	X	X	X _f
Subject VAS Pain assessment	X	X	X	X	X			
Subject Assessment Questionnaire (regarding downtime, skin erythema, redness and scabs)		X	X	X	X	X		
Adverse Events	X	X	X	X	X	X	X	X
Subject Compliance	X	X	X	X	X	X	X	X
Post Treatment Care Instructions	X	X	X	X	X			

- A limited physical examination will be performed at Screening to support the eligibility determination. System review will include general appearance, and a routine physical examination, according to the standard of care and as customary for fractional treatments.
- At Screening, the review of concomitant medications should include those taken within the past year.
- All assessments on treatment days are to be performed prior to treatment; the assessments performed prior to Treatment 1 will be designated as Baseline.
- Treatment sessions 4 & 5 are optional for both treatment options, based on the investigator's assessment of the subject's response.

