10. SAMPLE SIZE CONSIDERATIONS

The rationale for sample size calculation was based on difference between treatments arms in the improvement post treatment in FWCS scores.

$$\text{Improvement} = FWCS_{6 \text{ months}} - FWCS_{Baseline}$$

$$\text{NIM} = Improvement_{Tixel} - Improvement_{Laser} \geq -0.5$$

The assumption that Tixel is non inferior as compared to Laser in the effectiveness as evaluated by FWCS 6 months after first treatment.

FWCS ranges from fine to deep wrinkles in a 1 to 9 scale.

Previous studies demonstrated that the standard deviation of the change in FWCS post 6 months is 0.75.

Assuming that the non-inferiority margin is $\text{NIM} \geq -0.5$, and the $SD = 0.8$ a sample size of 32 completers per group will enable to conclude that Tixel is non inferior to ResuFx with 95% confidence and with 80% power.

Taking into account a dropout rate of 20% a total of 40 cases per group should be recruited. To allow for the possibility of a higher dropout rate a total of 41 cases per group will be recruited.

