11.2 Primary Performance Endpoint

FWCS scores will be summarized per subject and time point. Changes from baseline to the last follow-up visit will be summarized as well. For analyzing the changes over time within each arm, the Repeated

measures or Friedman paired test followed by Dunn's post hoc test (as appropriate based on Shapiro and Wilk test for normality) will be applied. For comparison between devices two-sample T-test or Non-parametric, Mann-Whitney Rank sum test (as is appropriate) will be applied.

In addition, in order to keep the study's power, data of the two sites will be pooled together and an Analysis of Covariance (ANCOVA) model will be applied for analyzing the primary endpoint, with adjustment to suspected confounders (baseline measure and site).

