11.2.1 Safety Assessment

Frequency and incidence of physical and dermatological examinations will be summarized.

Adverse events will be reported in tabulated format based on all ITT (intent to treat data set).

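### The primary between-device comparison has no effectiveness analysis set and no rule for missing final scores, although the sample size allows for 20% dropout

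*Combined protocol and SAP*

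**What the plan says.** Section 10 bases the trial on a single change in FWCS from baseline to 6 months, with a 0.5-point margin. It reports that "the standard deviation of the change in FWCS post 6 months is 0.75", uses 0.8 instead, and concludes that "a sample size of 32 completers per group will enable to conclude that Tixel is non inferior to ResuFx". The stated power is 80% and the stated confidence level is 95%. It then allows for 20% dropout to reach 40 per group, and recruits 41.

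Section 11.2 says of the outcome: "Changes from baseline to the last follow-up visit will be summarized as well". Devices are compared by a two-sample t-test or Mann-Whitney test, and an ANCOVA adjusted for baseline and site is added on the pooled sites. The repeated-measures or Friedman analysis in the same section concerns change within an arm, not the difference between arms.

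No analysis set is named for effectiveness, and nothing is said about missing scores. The only named set is in section 11.2.1, where adverse events are tabulated "based on all ITT (intent to treat data set".

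The flowchart in section 9 schedules photographs at all eight visits. Sections 2.3 and 2.4 have three blinded assessors score FWCS from images only. The flowchart marks that blinded reading at Visits 1 and 8 only, which agrees with the two data points per subject in section 2.1.

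**The concern.** A t-test, Mann-Whitney test or ANCOVA on one change score cannot use a subject whose final score is missing. Where the plan is silent, the comparison is therefore restricted to those who have the final score. That restriction is unbiased only if dropout is unrelated to response, given baseline and site. In an elective cosmetic study, subjects may leave because of side effects or disappointment, so this cannot be taken for granted. The documents give no reasons for dropout.

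The alternative is to read last follow-up as the last visit attended. Outcomes at 1, 3 and 6 months would then be pooled as one endpoint. That reading would also need blinded scores at Visits 6 or 7, which the flowchart does not mark, and it would still find no follow-up score for a subject lost before Visit 6. Because neither reading is fixed in advance, the choice could be made after the data are seen. In a non-inferiority trial, selective loss of poor responders from the test arm moves the result towards success.

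**Working it through.** **Inputs.** From section 10: margin 0.5, SD 0.8, 32 completers per group, 20% dropout, 41 recruited per group. From section 11.1: two-tailed tests at 5%. Assumed, because the documents do not give them: a true difference of 0 for the sample size, the gap between dropouts and completers, the correlation rho between Visit 7 and Visit 8 changes, and the share of dropouts who reach Visit 6 or 7.

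**The plan's own figure.** n per group = 2 × 0.8² × (1.645 + 0.842)² / 0.5² = 31.7, so 32 at one-sided 5% and 80% power. Then 32 / 0.8 = 40. Both figures reproduce, so the dropout inflation is correct. At one-sided 2.5% the same formula gives 41 completers.

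**Subjects lost from the comparison.** 0.20 × 82 = 16.4, about 16, or about 8 of 41 per arm. If only 2 × 32 = 64 complete, the loss is 82 − 64 = 18.

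**Bias.** Let dropouts improve by D points less than completers of the same arm. With 20% loss, the completers' mean is too favourable by 0.20 × D. The bias in the arm difference is 0.20 × (D for Tixel − D for laser).

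- D for Tixel 0.4, laser 0: bias 0.08, or 16% of the margin.
- D for Tixel 0.8, laser 0: bias 0.16, or 32% of the margin.
- Equal D in both arms: bias 0.
- D larger for laser: bias against Tixel.

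**False non-inferiority when the true deficit equals the margin.** SE = 0.8 × √(2/32) = 0.20. Probability = 1 − Φ(z − bias/0.20).

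| Bias | One-sided 5% (z = 1.645) | One-sided 2.5% (z = 1.960) |
|---|---|---|
| 0 | 5% | 2.5% |
| 0.08 | 1 − Φ(1.245) = 10.7% | 1 − Φ(1.560) = 5.9% |
| 0.16 | 1 − Φ(0.845) = 19.9% | 1 − Φ(1.160) = 12.3% |

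**What Visit 7 readings could recover.** In a simulation of 20,000 runs per rho, Tixel dropout depended on the Visit 7 change, laser dropout was random, every subject had a Visit 7 reading, and the true deficit was 0.50. Error was set at one-sided 5%.

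| rho | Deficit, completers only | Error, completers only | Deficit, Visit 7 used | Error, Visit 7 used |
|---|---|---|---|---|
| 0.5 | 0.43 | 10.2% | 0.50 | 5.7% |
| 0.7 | 0.40 | 13.2% | 0.50 | 5.7% |
| 0.9 | 0.37 | 17.0% | 0.50 | 5.9% |

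This is the favourable case for the remedy, since the variable that drives dropout is observed for everyone.

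**Power gain.** Effective n = nc / (1 − rho² × (1 − nc/nv)), with nc = 33 subjects per arm having Visit 8 and nv the number having Visit 7 or 8. Completers alone give 81.4% power at one-sided 5%.

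- Half of dropouts recovered, rho 0.5: 33 / (1 − 0.25 × (1 − 33/37)) = 33.9, power 82.4%.
- All recovered, rho 0.9: 33 / (1 − 0.81 × (1 − 33/41)) = 39.2, power 86.9%.

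The gain is about 1 to 5.5 percentage points.

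**The case against.** Several stronger readings are tempting, and the documents do not support them.

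- **That the plan commits to a completer analysis.** The word completers appears only in the sample-size section, where inflating for dropout is routine and defines no analysis population. Section 11.2 arrives at a completer comparison by silence.
- **That all 16 to 18 lost subjects have usable follow-up images.** Visit 6 and 7 photographs exist only for subjects who reach those visits. The timing of dropout is not given, so the recoverable number lies anywhere from none to all.
- **That the plan favours Tixel, or that its error rate is 11% to 20%.** Those figures need informative loss in the Tixel arm alone and a one-sided 5% test. The protocol's background describes Tixel as designed for fewer side effects and more comfort, so loss weighted towards the laser arm is also arguable, and that would bias against Tixel.

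It can also be said that two blinded time points per subject is a deliberate design choice. It is, but it does not settle what happens when the second is missing.

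A further fair objection is that a mixed model over Visits 6 to 8 assumes data missing at random and learns nothing about outcome in subjects lost during treatment, where side effects might drive loss. This stands, and it is why a separate sensitivity analysis is needed.

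**Conclusion.** The concern holds as a gap in the analysis plan. Section 10 expects 20% loss, and section 11.2 provides tests that cannot use the lost subjects, with no stated set and no rule. The arithmetic behind 32 and 40 is sound.

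The certain part is that about 16 of 82 subjects leave the comparison at the planned dropout rate, or that visits are mixed under the other reading. The bias is conditional: 0.08 to 0.16 points under the one-sided pattern assumed above, zero under equal informative loss, and reversed if laser dropouts are the poorer responders. The reason to act is protection against bias. The power gain is modest and rests on assumed correlations and on how many dropouts reach Visit 6 or 7. The change should be made, but the documents do not show that the result will be wrong without it.

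**What to change.** In section 11.2:

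1. Define the primary effectiveness set as all randomised and treated subjects, analysed as randomised, and define the primary visit.
2. Have the same blinded assessors also score the photographs already scheduled at Visits 6 and 7.
3. Replace the change-score test and ANCOVA as primary with a mixed model for repeated measures: arm, visit, arm-by-visit, baseline FWCS and site. Take the arm difference at the primary visit, with its confidence interval, against the 0.5-point margin.
4. Report the completer ANCOVA as supportive. Making it a second condition for success could only lower power.
5. Add a not-missing-at-random sensitivity analysis, for example a tipping-point analysis, for subjects lost before Visit 6, whom the model cannot recover.

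Three matters must be reconciled before the margin is applied:

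- **Sign.** Section 10 defines improvement as the 6-month score minus baseline on a scale that rises with wrinkle depth. Benefit is then negative, and the stated inequality does not test inferiority of Tixel.
- **Timing.** Section 10 places the endpoint 6 months after first treatment, while the flowchart puts the 6-month follow-up, Visit 8, at 42 weeks from first treatment.
- **Confidence level.** The 32 in section 10 needs one-sided 5%, while section 11.1 specifies two-tailed 5%.

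The cost is SAP wording and blinded reading of two more visits per subject: at most 2 × 82 = 164 subject-visits per assessor, or 3 × 164 = 492 across the three. The number of images per visit is not given. No extra visit or procedure is needed. The estimate may be slightly less favourable than one based on completers.

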5.1. Number of Subjects

A total of 82 subjects will be recruited to the study. They will be randomly split to two separate arms (41/arm) in each site, and undergo periorbital fractional treatments.

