11. STATISTICAL METHODS

11.1 General

All measured variables and derived parameters will be listed individually and, if appropriate, tabulated by descriptive statistics.

For categorical variables summary tables will be provided giving counts and percentages.

For continuous variables summary tables will be provided giving count, arithmetic mean, standard deviation, median, 25th and 75th percentile, minimum and maximum of variables by device.

All tests will be two-tailed, and a p-value of 5% or less will be considered statistically significant.

The data will be analyzed using the SPSS version 925.0.

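### The 32 completers per arm give 80% power only at one-sided 5%; under the plan's own two-tailed 5% rule the power is about 69–71%

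*Combined protocol and SAP*

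**What the plan says.** Section 10 sizes the trial for non-inferiority on the change in FWCS, with the margin written as "Improvement_{Tixel} - Improvement_{Laser} \geq -0.5". It reports from earlier studies that "the standard deviation of the change in FWCS post 6 months is 0.75", but uses an SD of 0.8 in the calculation. It concludes that "32 completers per group will enable to conclude that Tixel is non inferior to ResuFx with 95% confidence and with 80% power". It does not say whether the 95% confidence is one- or two-sided, and it gives no numerical true difference. On recruitment it says "Taking into account a dropout rate of 20% a total of 40 cases per group should be recruited", then raises this to 41 per group, in line with the total of 82 in Section 5.1.

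Section 11.1 sets the level for the analysis: "All tests will be two-tailed, and a p-value of 5% or less will be considered statistically significant".

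Section 11.2 names a two-sample t-test or Mann-Whitney test for the comparison between devices, and adds an ANCOVA adjusted for baseline and site. It describes no confidence bound to set against the margin and no one-sided test. No other section exempts the non-inferiority comparison from the two-tailed rule.

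**The concern.** A non-inferiority conclusion uses only one end of the confidence interval. A two-tailed 5% rule corresponds to a two-sided 95% interval, so the error rate in the non-inferiority direction is 2.5%. A one-sided 95% bound corresponds to a two-sided 90% interval and an error rate of 5%. The completer number in Section 10 looks like the second, and the testing rule in Section 11.1 is the first.

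Two things are at stake. If Section 11.1 governs, the stated power is not delivered, and the risk that an equally effective Tixel misses non-inferiority rises from 20% to about 30%. If the one-sided 5% level governs, the false-positive rate in the non-inferiority direction is twice what Section 11.1 implies. While both stand, the level could be chosen after the data are known.

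**Working it through.** **Inputs.** From Section 10: margin 0.5, SD 0.8 (0.75 as a sensitivity value), power 80%, 32 completers per arm, dropout 20%. From Sections 5.1 and 10: 41 recruited per arm, 1:1. From Section 11.1: two-tailed 5%. Assumed: true difference 0, which reproduces the plan's number. With a true difference of 0 the calculation is symmetric, so it does not depend on the sign convention for improvement.

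**Formula.** Completers per arm: n = 2 × (z_α + z_power)² × SD² / margin², with z_power = 0.842 for 80%.

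**The plan's figure.** One-sided 5%, z_α = 1.645:

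n = 2 × (1.645 + 0.842)² × 0.64 / 0.25 = 31.7, so 32. This matches Section 10. Dropout: 32 / 0.80 = 40, which also matches.

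**Under Section 11.1.** 2.5% in the non-inferiority direction, z_α = 1.960:

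n = 2 × (1.960 + 0.842)² × 0.64 / 0.25 = 40.2, so 41 (42 with the t distribution). With 20% dropout, 41 / 0.80 = 51.25 and 42 / 0.80 = 52.5, so 52 or 53 recruited per arm against the planned 41.

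**Power with the planned numbers.** At 32 per arm the standard error is 0.8 × √(2/32) = 0.20, and 0.5 / 0.20 = 2.50. Normal approximation: Φ(2.50 − 1.645) = 80.4% and Φ(2.50 − 1.960) = 70.5%. The t figures use the noncentral t distribution, with 62 degrees of freedom at 32 per arm.

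| Completers per arm | SD | Level | Power, t | Power, normal |
|---|---|---|---|---|
| 32 | 0.80 | one-sided 5% | 79.6% | 80.4% |
| 32 | 0.80 | two-tailed 5% | 69.2% | 70.5% |
| 33 (41 less 20%: 32.8) | 0.80 | two-tailed 5% | 70.6% | 71.9% |
| 41 (no dropout) | 0.80 | two-tailed 5% | 79.8% | 80.8% |
| 32 | 0.75 | two-tailed 5% | 74.7% | 76.0% |

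At the two-tailed level, 32 per arm reaches 80% only if the SD is about 0.71 or lower: 0.5 / (2.802 × √(2/32)) = 0.714.

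**Effect on the conclusion.** With a standard error of 0.20, the one-sided 95% bound clears the margin if Tixel trails by less than 0.5 − 1.645 × 0.20 = 0.17 points. The two-sided 95% interval clears it only if Tixel trails by less than 0.5 − 1.960 × 0.20 = 0.11 points. An observed deficit between 0.11 and 0.17 would be non-inferior under one reading and not under the other.

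**Baseline adjustment.** If ANCOVA reduces the SD to 0.8 × √(1 − r²), where r is the correlation between baseline and change, two-tailed power at 32 per arm (t) is 73.2% for r = 0.3, 76.6% for r = 0.4 and 81.1% for r = 0.5. The plan states no value of r.

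**The case against.** The best defence is that Section 10 contains no arithmetic error. Read as a one-sided 95% bound, its confidence statement gives exactly 32. Section 11.1 can then be taken to govern ordinary difference tests and their p-values, which is how the between-device tests in Section 11.2 are described, while the non-inferiority conclusion rests on a confidence bound. On that reading both sections stand and the 80% is correct. The defence can add that the 69–71% depends on conditions: SD 0.8 rather than the cited 0.75, no covariate adjustment, and a true difference of zero.

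Part of this stands. The formula was applied correctly, so the fault is a conflict between sections. The power figure is conditional: at SD 0.75 it is 74.7–76.0%, and 36 or 37 completers per arm would be enough, which 41 recruited could supply with about 10–12% dropout. ANCOVA could recover the loss if r is about 0.5.

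The rest does not remove the problem. The one-sided reading has to be inferred from the sample size, while the two-tailed rule is written down and covers all tests. Section 11.2 offers no separate non-inferiority rule to which an exception could attach. The cited SD does not restore 80%. The ANCOVA does so only under a correlation that the plan neither states nor used in sizing. A small true disadvantage for Tixel works the other way: at a true deficit of 0.1, the two-tailed requirement is 40.2 × 0.25 / 0.16 = 62.8, so 63 completers per arm.

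**Conclusion.** The concern holds. At margin 0.5, SD 0.8 and true difference 0, the stated 80% power belongs to a one-sided 5% test. The rule written in Section 11.1 gives 69.2% (t) or 70.5% (normal) with 32 completers per arm, a shortfall of about 10 percentage points. An equally effective Tixel would then miss non-inferiority about three times in ten.

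The power and sample-size figures are certain given those inputs. What the authors intended is not, because a one-sided 95% bound is a possible reading of Section 10. But that reading needs an exception the plan does not contain, so text must change whichever level was meant. Since the choice sets the success criterion for the primary endpoint, it must be corrected before unblinding.

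**What to change.** Choose one level for the primary non-inferiority comparison and state it identically in Sections 10, 11.1 and 11.2.

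- **Option (a), keep the two-tailed rule.** State in Section 10 that 32 completers per arm give about 69–71% power at SD 0.8 and true difference 0, with non-inferiority concluded from a two-sided 95% interval.
- **Option (b), keep the 32 and the 80%.** State in Sections 10 and 11.1 that the primary test is one-sided at 5%, equivalent to a two-sided 90% interval, and exempt it from the two-tailed rule.

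Under either option, say in Section 11.2 which confidence limit is compared with the margin, write the assumed true difference of zero into Section 10, and make the baseline- and site-adjusted ANCOVA already planned the primary analysis. If a power gain from adjustment is claimed, state the assumed correlation: about 0.5 is needed to bring two-tailed power back to about 81%.

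The cost is wording, with no extra subjects or visits. Option (a) shows a less favourable power figure. Option (b) openly accepts a 5% rather than 2.5% false-positive rate in the non-inferiority direction.

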11. STATISTICAL METHODS

11.1 General

All measured variables and derived parameters will be listed individually and, if appropriate, tabulated by descriptive statistics.

For categorical variables summary tables will be provided giving counts and percentages.

For continuous variables summary tables will be provided giving count, arithmetic mean, standard deviation, median, 25th and 75th percentile, minimum and maximum of variables by device.

All tests will be two-tailed, and a p-value of 5% or less will be considered statistically significant.

The data will be analyzed using the SPSS version 925.0.

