Wrinkles, in general, are reported to appear in people even younger than thirty years of age³. In the same manner as any other facial wrinkle, periorbital wrinkles increase gradually and affect one's appearance and facial expression. Such effect also reflects on quality of life, due to impact on social interactions, occupational functioning and self-esteem in general⁴. Therefore, periorbital wrinkle reduction treatments are sought by many worldwide.

Study Title:

A Prospective, Randomized, Double Arm, Controlled Study with Blinded Assessment To Evaluate The Safety And Effectiveness Of The Tixel Fractional System In The Treatment Of Periorbital Wrinkles In Comparison With Fractional Laser

Investigational Product:

Tixel by Novoxel, model No. TXLD0002

The Tixel system was designed to fulfill a clinical need for fractional treatment for aging skin with reduced side effects and safety related complications, associated with current available treatment modalities, together with increasing patient comfort. The Tixel employs a thermo-mechanical

¹ “A Prospective Split-Face Comparative Study of Periorbital Wrinkle Treatments: Fractional Erbium Doped Yttrium Aluminum Garnet Laser Intense Pulsed Light, and Topical 0.1% Tretinoin Cream”, So Eun Park, Sang Seok Kim, Chul Woo Kim, Young Her, Department of Dermatology, Kangdong Sacred Heart Hospital, Hallym University College of Medicine, Seoul,

¹Department of Dermatology, Kangwon National University Hospital, Kangwon National University School of Medicine, Chuncheon, Korea

² <https://www.mayoclinic.org/diseases-conditions/wrinkles/symptoms-causes/syc-20354927>

³ “Wrinkles”, Juan Manríquez, Daniela Majerson Grinberg, and Claudia Nicklas Diaz, Clinical Evidence 2008;12:1711

⁴ Gupta MA, Gupta AK. Photodamaged skin and quality of life: reasons for therapy. J Dermatol Treat 1996;7:261–264.

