The following assessment method will be applied by the blinded assessors (by images only):

- FWCS - Fitzpatrick Wrinkle Classification System

2.4.Secondary Outcome Endpoints

The following criteria will be assessed as secondary outcome endpoints:

- Secondary Effectiveness/Performance shall be assessed and quantified by a handling physician (one of the team's investigators of the study).

The following assessment methods will be applied (frontal clinical assessment or by images):

- FWCS - Fitzpatrick Wrinkle Classification System
- GAIS - Global Aesthetic Improvement Scale Assessment
- WAS - 5-point Wrinkle Assessment Scale
- Subject Experience
- Pain Level VAS Scale
- Subject Subjective Downtime Assessment

- Subject redness, edema and crust assessment (time for resolution)
- End-User Experience Assessment

Clinic Visits Baseline, 4wk, 8wk, (optional 12wk and 16wk), 20wk, 28wk, 42wk

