11.3 Secondary endpoints

All parameters below will be summarized at baseline condition and all post-baseline conditions. The change from baseline to the last follow-up will be analyzed using Wilcoxon paired test.

The following secondary endpoints will be summarized in appropriate tables by device and visit:

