11.3.1.8 End-User Experience Assessment

11.3.1.9 Repeated measures or Friedman's test (as is appropriate) will be applied for analyzing the changes within side (device) and .The two-sample T-test or Non-parametric Mann-Whitney Rank test (as is appropriate) will be applied for comparative analysis of the changes between the devices.

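### Each of up to eight unranked secondary device comparisons is called significant at 5%, so equal devices have up to about a one-in-three chance of showing at least one false difference at a single visit

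*Combined protocol and SAP*

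**What the plan says.** Section 11.1 (General) fixes the significance rule for every analysis: "All tests will be two-tailed, and a p-value of 5% or less will be considered statistically significant".

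Section 2.4 introduces the secondary list with "The following criteria will be assessed as secondary outcome endpoints". Section 11.3 repeats the same eight items as 11.3.1.1 to 11.3.1.8: physician-rated FWCS, GAIS, WAS, subject experience, VAS pain, subject-rated downtime, time to resolution of redness, edema and crust, and end-user experience. Neither list states an order of importance.

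Three kinds of analysis are attached to these endpoints:

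- Section 11.3: "The change from baseline to the last follow-up will be analyzed using Wilcoxon paired test".
- Section 11.3.1.9, repeated measures or Friedman: "will be applied for analyzing the changes within side (device)".
- Section 11.3.1.9, two-sample t-test or Mann-Whitney: "will be applied for comparative analysis of the changes between the devices".

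Only the third compares the devices. The visit for that comparison is not given. Section 11.3 also says "The following secondary endpoints will be summarized in appropriate tables by device and visit". The only multiple-comparison procedure named anywhere is Dunn's post hoc test in section 11.2, and it concerns change over time within an arm for the primary measure.

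**The concern.** The plan does more than leave out an adjustment. It says positively that any p-value of 5% or less will be called significant, and it supplies up to eight device comparisons to which that label can attach. The 5% rate then holds for each test but not for the set.

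This matters because the primary question is non-inferiority: "The assumption that Tixel is non inferior as compared to Laser in the effectiveness as evaluated by FWCS 6 months after first treatment". Meeting it shows that Tixel is not worse by more than the margin. Evidence that Tixel is better on something would have to come from elsewhere, and the secondary endpoints are an obvious place to look. VAS pain, downtime and time to resolution bear on the device's stated design purpose of "reduced side effects and safety related complications, associated with current available treatment modalities, together with increasing patient comfort", yet they sit unranked among the eight. A nominally significant result on one of them would be open to the reply that it was picked from eight after the fact, even if the advantage were real.

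**Working it through.** **Plan's own figure.** The documents give no overall error rate for the secondary endpoints, so there is none to reproduce. The one calculated figure, 32 completers per group in section 10, concerns the primary. It reproduces at one-sided 5% with margin 0.5, SD 0.8 and 80% power: 2 × (1.645 + 0.842)² × 0.8² / 0.5² = 31.7, rounded up to 32. It does not enter the calculation below.

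**Inputs.**
- Per-test level: two-sided 0.05 (section 11.1).
- Number of device tests, k: at most 8 at one visit (sections 2.4 and 11.3). The t-test and Mann-Whitney are alternatives, so they count once.
- Correlation between endpoints: not in the documents. Assumed, range 0 to 0.9.
- Number of comparison visits: not in the documents. Assumed to be one as the base case, with two and three as sensitivity.

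**How many endpoints can be tested as changes?** The flowchart in section 9 shows:

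| Endpoint | Scheduled | Visit 1 and Visit 8? |
|---|---|---|
| FWCS | Visits 1–8 | yes |
| WAS | Visits 1–8 | yes |
| Subject experience | Visit 1, one of Visits 3–6, Visit 8 | yes |
| GAIS | Visits 2–8 | no |
| VAS pain | Visits 1–5 | no |
| Downtime; redness and scabs (one questionnaire) | Visits 2–6 | no |
| End-user experience | no row | no |

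So eight is an upper count at one visit. Three endpoints support a change from baseline to last follow-up.

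**Chance of at least one p ≤ 0.05 if the devices are equal, independent tests:** 1 − 0.95^k.
- k = 8: 1 − 0.95⁸ = 0.337. Expected number of false positives: 8 × 0.05 = 0.4.
- k = 3: 1 − 0.95³ = 0.143.
- k = 13: 0.487; k = 14: 0.512. Fourteen independent tests are needed to pass one half.

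**Correlated tests.** Simulation of eight equally correlated normal test statistics, two-sided 0.05:

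| Correlation | Any difference | In Tixel's favour only |
|---|---|---|
| 0 | 33.7% | 18.3% |
| 0.3 | 30.0% | 15.2% |
| 0.5 | 25.0% | 12.6% |
| 0.7 | 19.0% | 9.5% |
| 0.9 | 12.0% | 6.0% |

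**Several visits.** With eight endpoints compared at each visit, visit correlation 0.7 and endpoint correlation 0.3, the figure is 45% for two visits and 55% for three. With endpoint correlation 0.5 it is 38% and 47%. These are illustrations, since the flowchart does not schedule every endpoint at every visit.

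**For scale.** A Bonferroni level of 0.05/8 = 0.00625 gives 1 − (1 − 0.00625)⁸ = 4.9%.

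**The case against.** The strongest case against is that this is a small matter. The primary is untouched. The documents announce no secondary claim, and section 11.3 speaks first of summary tables. Physician FWCS, WAS and GAIS all rate the same wrinkles, so independence is the extreme case. A false result in Tixel's favour, the direction that would support a sponsor claim, is at most 18.3%. A very small p-value, say below 0.00625, would survive adjustment anyway. All of this stands and limits the size of the point. It does not remove it, because section 11.1 still attaches the word significant to every such result and nothing calls the endpoints exploratory.

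A reader might infer three stronger things that the documents do not support:

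- *A false secondary device claim is likely.* At one visit no figure reaches one half. It is passed only under assumptions such as comparison at three visits, which the plan does not specify.
- *The within-device tests multiply the problem.* Counting one per arm for each endpoint gives 8 + 16 = 24 tests and 1 − 0.95²⁴ = 70.8%. But equal devices can both work. A significant change within an arm is then a correct finding and not a false device difference.
- *The sponsor plans comfort and side-effect claims from this trial.* The synopsis sentence describes what the device was designed for. It names no trial claim and sets no order of endpoints.

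**Conclusion.** The point holds in a limited form. Applied as written, the plan gives equal devices a chance of up to about one in three of at least one nominally significant secondary difference at a single visit. The figure rests on one device test per endpoint and on assumed correlations: 33.7% at zero correlation, 19% to 30% at 0.7 to 0.3, and about 14% if only the three endpoints with both Visit 1 and Visit 8 entries are tested. Every one of these exceeds 5%. The true count cannot be settled from the documents because the comparison visit is not stated, and several visits would push the figure up. What is affected is the standing of secondary device differences; the non-inferiority conclusion is not.

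**What to change.** In sections 11.1 and 11.3:

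1. Limit the term *statistically significant* to the primary analysis and, only if primary non-inferiority is shown, to any secondary endpoints the sponsor names in a fixed order before unblinding. Each is tested at two-sided 5%, stopping at the first failure. The choice and order are the sponsor's, and naming none is acceptable.
2. Give each named endpoint a comparison visit or summary measure. VAS pain is recorded only at treatment visits and downtime has no baseline, so these would be compared as values and not as changes from baseline to last follow-up.
3. Report all other secondary between-device comparisons, and all within-device tests, as estimates with 95% confidence intervals and nominal p-values, described as descriptive.

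Step 1 needs a written decision rule for non-inferiority. Section 10 gives the margin, but section 11.2 does not say how the analysis will be judged against it.

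The cost is SAP wording, with no change to sample size or data collection. The downside is that secondary results outside the pre-named sequence can no longer be called significant.
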